14.0 BIOSTATISTICS

Statistical Plan for Evaluation of Primary and Secondary Endpoints

A total of 81 patients will be accrued to this study (10 melanoma patient and 71 bladder

patients). Only patients with bladder cancer will be evaluated for the primary and secondary objectives as described here. Melanoma and bladder patients will be evaluated for the exploratory endpoints described in the next section. The primary clinical objective is to determine the confirmed response rate defined per RECIST 1.1 to protocol therapy. Of note, atypical responses are well known to occur in patients treated with immune checkpoint blockade, including early radiographic progression due to immune infiltration followed by subsequent radiographic response and durable clinical benefit. Thus, patients who have early radiographic progression but are felt to be clinically benefitting and convert to confirmed stable disease, partial response, or complete response will be considered progression-free and will be assigned a best confirmed overall response of SD, PR, or CR.

The primary correlative objective is to obtain information on mutational load and obtain preliminary prospective data on whether this factor is predictive of response to immunotherapy. Patient's mutational load will be assessed using tissue prior to treatment and the number of mutations will be calculated. We will perform a nonparametric receiver operator characteristic (ROC) curve analysis with mutational load as a continuous measure and estimate the area under the curve (AUC) to assess the detectability of responders. The cutoff point will be identified using Youden's index. It is estimated that approximately 85% of enrolled patients will be considered evaluable for both the clinical and research (WES, RNAseq) study endpoints, with an approximate 10% failure rate related to the biopsy, biopsy sample preparation and sequencing, and an approximate 5% failure rate for clinical reasons (i.e. patient replaced for clinical reasons and non-evaluable for response). Based upon these calculations, we estimate that we will have approximately 60 bladder patients and approximately 8 melanoma patients with both clinical and research (genomic) data for analysis, consistent with the protocol statistical plan. With 60 bladder patients, 80% power and 5% significance level, we can detect a difference in AUC from: 0.5 to 0.7 if the response rate 50%; 0.5 to 0.71 if the response rate is 33%; and from .5 to 0.73 if the response rate is 25%.

All patients who receive at least one dose of nivolumab will be evaluated for the primary clinical endpoint defined as the proportion of patients who achieve a confirmed complete or partial response based on RECIST 1.1 criteria. Patients who develop rapid symptomatic disease progression or drop out early due to death will be treated as progressive disease. Patients who develop early toxicities that require treatment delay or discontinuation will continue to be evaluable for response on study.

Patients who receive at least 1 dose of nivolumab and have adequate biopsy material for whole exome sequencing and adequate sequencing data for determination of mutation burden will be considered evaluable for clinical and correlative objectives. Tumor mutation burden and neo-antigen score will be determined for each patient enrolled as described in section Appendix 3. We will perform the same analysis for patients according to their neo-antigen score (as described in Appendix 3). This analysis of the relationship between mutation burden and response rate will be performed for each tumor type independently.

It is anticipated that 4-5 patients per month will be accrued per cohort and accrual will be completed within two years.

Exploratory Endpoints

Patient Evaluation & Statistics for Clinical Endpoints

All patients who received at least one dose of nivolumab will be evaluated for clinical endpoints including tumor response (ORR, DOR, OS and PFS), rate of grade 3/4 toxicity, and survival. Patients who (1) develop rapid symptomatic disease progression, or (2) drop out early due to death will be treated as non responders. Patients who develop early toxicities that require treatment delay or discontinuation will continue to be evaluated for response on study. Kaplan-Meier methodology will be implemented to estimate the median survival time, median progression-free survival, and the PFS and OS rates. Overall survival will be defined as the time from treatment start to death or last follow-up; progression-free survival will be defined as the time from treatment start to the date of progression/death or last follow-up.

Exploratory Tumor and Peripheral Blood Immune Markers

The following endpoints will be evaluated in an exploratory fashion as sample availability permits. Descriptive statistics and graphical measures will be employed. Details related to methods are described in Appendix 3.

- 1. Compare tumor characteristic (mutation burden, neo-antigen score, PD-L1, TCR repertoire, immune infiltrate) between pre-treatment and on-treatment (optional) tumor biopsies**

We aim to collect ~ 20 matched tumor biopsies (pre-treatment/on treatment) (target 10 per tumor type), and the comparison will be primarily descriptive and hypothesis generating. Mean and median mutation burden will be quantified in both pre-treatment and on-treatment biopsies. The difference in mean and median between these timepoints will be compared using nonparametric tests such as Wilcoxon signed rank test. Qualitative comparisons (i.e. types of mutations, neo-antigens) will be descriptive. Adaptive Biotechnologies and MedGenome will serve as collaborators for this TCR analysis.

- 2. Evaluate tumor PD-L1 expression across range of mutation burden/predicted neo-antigens.**

PD-L1 expression will be evaluated in pre-treatment and on-treatment biopsies. PD-L1 expression on tumor cells will be graded as positive or negative, according to the most up to date standards for the assay in use. The tumor positivity of PD-L1 expression (on either tumor or immune cells) will be compared in the pre- and post-treatment biopsies using a Wilcoxon signed rank test. Comparisons of immune infiltrate and TCR repertoire will be descriptive. Summary statistics will be generated and differences between mutation burden or neo-antigen score as they relate to PD-L1 expression will be compared using the Wilcoxon rank sum test.

- 3. Evaluate TCR repertoire across a range of mutation burdens/predicted neo-antigen scores.**

Tcell receptor frequencies in the repertoire per patient will be tabulated. Summary statistics will be generated and differences between mutation burden or neo-antigen score as they

relate to TCR repertoire will be compared using the Wilcoxon rank sum test. Adaptive Biotechnologies and MedGenome will serve as collaborators for this TCR analysis.

4. Evaluate for the presence of predicted neo-antigen specific T cells in peripheral blood samples.

Ex vivo and in vitro analysis of peripheral blood T cells will be employed to evaluate for the presence of predicted neo-antigen specific T cells as described in detail in appendix 3.

5. Compare IMPACT assay to whole exome sequencing for the evaluation of patients according to mutation burden.

The number of mutations quantified according to whole exome sequencing and according to IMPACT assay will be quantified and correlation analysis between whole exome analysis and IMPACT will be assessed. This will be exploratory. If a cutoff of high versus low mutation burden is determined from earlier analyses using the whole exome this will be used to guide the IMPACT preliminary analysis.

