2.0 OBJECTIVES AND SCIENTIFIC AIMS

Primary Correlative Objective: Obtain preliminary prospective data on whether mutational load is associated with RECIST 1.1 response to immunotherapy.

Primary Clinical Objective: Obtain prospective data on the overall response Rate (per RECIST 1.1) to 1) nivolumab monotherapy and 2) ipilimumab and nivolumab combination therapy in patients progressing on initial nivolumab monotherapy.

Secondary Clinical Objectives:

1. Evaluate duration of response (DOR), progression free survival (PFS), overall survival (OS), rate of grade 3/4 toxicity.
2. Evaluate ORR, DOR, PFS, OS according to the immune related RECIST criteria.

Secondary Correlative Objectives:

1. Obtain preliminary prospective data on whether neo-antigen score is associated with RECIST 1.1 response to immunotherapy.
2. Compare tumor characteristics (mutation burden, neo-antigen score, PD-L1, TCR repertoire, immune infiltrate) between pre-treatment and on-treatment (optional) tumor biopsies.
3. Evaluate tumor PD-L1 expression across range of mutation burden/predicted neo- antigens.
4. Evaluate TCR repertoire across a range of mutation burdens/predicted neo-antigen scores.
5. Evaluate for the presence of predicted neo-antigen specific T cells in peripheral blood samples.
6. Compare IMPACT assay to whole exome sequencing for the evaluation of patients according to mutation burden.

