Responses to ipilimumab are often delayed and may be seen after initial apparent disease progression. The unique pattern of disease response seen in patients with ipilimumab led to a retrospective study analyzing patients treated across several phase 2 trials. In this evaluation, improved survival was associated with a variety of disease response patterns such as patients who initially appeared to have progressive disease but later achieved response and those who had prolonged stable disease. To better reflect the distinct kinetics of response, the immune-related response criteria (irRC) were proposed.¹⁷ The irRC are undergoing prospective validation in ongoing clinical trials. IrRC may also have utility in nivolumab treated patients. A recent abstract at ASCO 2014 presented by F. Stephen Hodi described a survival benefit in patients treated with nivolumab who achieve responses by irRC, but not by traditional response criteria, compared to those who have disease progression by irRC.

Thousands of patients have been treated with ipilimumab and its toxicity profile is well described. The most severe irAE is generally considered to be an inflammatory colitis, which requires prompt treatment with steroids and, in some cases, anti-TNF-alpha therapy. Other side effects related to ipilimumab consist of hypophysitis, hepatitis, and dermatitis. Other rarer side effects have also been reported including peripheral neuropathy and uveitis. Published algorithms for the treatment of ipilimumab-related irAEs are available (<https://www.hcp.yervoy.com/pages/rems.aspx>).

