analysis. Patients who develop early toxicities that require treatment delay or discontinuation will continue to be evaluated for response on study and response will be determined based upon radiographic evaluation. In the unlikely scenario where a patient is lost to followup in the first 12 weeks on study and a determination of response by either radiographic findings, clinical progression, or death related to disease cannot be made, this patient would be considered non-evaluable.

This analysis of the relationship between mutation burden and response rate will be performed for each tumor type (melanoma vs. bladder) independently. A responder is defined as someone who achieves a confirmed complete or partial response based on RECIST 1.1 criteria. The cutoff point will be identified using Youden's index. These results will be examined in a descriptive manner in order to identify potential predictive measures. In addition, we will run the same analysis using the predicted neo-antigen score (as described in Appendix 3) and test if predicted neo-antigen burden is predictive of response.

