have early radiographic progression but are felt to be clinically benefitting and convert to confirmed stable disease, partial response, or complete response will be considered progression-free and will be assigned a best confirmed overall response of SD, PR, or CR.

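### The primary response rate is labelled RECIST 1.1 but also credits responses after early radiographic progression, with no strict analysis and no stated cut-off at crossover

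*Combined protocol and SAP*

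**What the plan says.** **Endpoint.** Section 14.0: "The primary clinical objective is to determine the confirmed response rate defined per RECIST 1.1 to protocol therapy". The same section defines the endpoint, for all patients given at least one dose of nivolumab, as "defined as the proportion of patients who achieve a confirmed complete or partial response based on RECIST 1.1 criteria".

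**ROC label.** Section 4.1: "A responder is defined as someone who achieves a confirmed complete or partial response based on RECIST 1.1 criteria".

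**Exception.** Section 12.0 names RECIST 1.1 as the response criterion and then turns to patients who "have early radiographic progression but are felt to be clinically benefitting". Section 14.0 carries the same rule: those who "convert to confirmed stable disease, partial response, or complete response will be considered progression-free and will be assigned a best confirmed overall response"; the categories named are SD, PR and CR. Both sections give immune infiltration followed by genuine response as the reason.

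**Immune-related criteria.** Section 3.0 explains that immune-related criteria were proposed because responses can follow apparent progression. It cites nivolumab patients "who achieve responses by irRC, but not by traditional response criteria". Section 2.0 lists a separate secondary objective: "Evaluate ORR, DOR, PFS, OS according to the immune related RECIST criteria".

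**Crossover.** Section 2.0 splits the primary clinical objective into response to nivolumab monotherapy and response to the combination after progression on monotherapy. Sections 4.1 and 14.0 speak only of response to protocol therapy.

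**PFS.** Section 12.0 uses the first confirmed progression as the event. The exploratory part of section 14.0 uses the date of progression and does not require confirmation.

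**The concern.** The label and the counting rule do not describe the same quantity. A reader shown a confirmed RECIST 1.1 response rate will assume that the best response was reached before progression. Under the rule it need not have been, and the plan has no analysis without the rule. The immune-related secondary objective also loses part of its purpose, since the feature that sets it apart is already in the primary.

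The terms for entering the rule (early; felt to be benefitting) are undefined in an open-label study. Section 16.1.2 makes responses subject to committee review but does not say which definition the committee applies. Two analysts with the same scans could report different primary rates.

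The rule also sets no end point at the first combination dose. Bladder patients may progress on nivolumab and then receive the combination, so the text does not settle under which part of the primary objective a later response belongs, or whether it counts as a response for the ROC. Section 4.1 does not repeat the exception for the ROC responder. That it carries over is an inference, though a strong one: section 14.0 states the rule ahead of both primary analyses and gives no other source for the label.

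**Working it through.** **1. The plan's own figures.** Section 14.0 gives 71 bladder patients and 85% evaluable: 71 × 0.85 = 60.35, about 60, as stated. It also gives detectable AUCs of 0.70, 0.71 and 0.73 at response rates of 50%, 33% and 25% (60 patients, 80% power, 5% level, sidedness not stated). I used the binormal (Obuchowski) variance, with n1 responders, n0 non-responders, r = n0/n1 and a = 1.414·Φ⁻¹(AUC):

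V = 0.0099·exp(−a²/2)·[(5a² + 8) + (a² + 8)/r]/n1

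Power = Φ{[(AUC − 0.5) − 1.96·√V(0.5)]/√V(AUC)}

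For 15/45 and AUC 0.73: √V(0.5) = 0.0839, √V(0.73) = 0.0816, and (0.23 − 1.96 × 0.0839)/0.0816 = 0.80, so power is 78.9%. For 20/40 and 30/30 it is 78.5% and 79.6%. The plan's figures reproduce with a two-sided test, so this point is about definition and not about arithmetic.

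**2. Effect on the response rate.** A patient who responds before progression is untouched by the rule. A patient who converts to PR or CR after progression is added. Conversion to SD changes PFS only. The count can therefore only stay or rise, by 1/71 = 1.4 points per converter. The documents give no conversion rate, so both the base and the number of converters below are assumptions.

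| Counted as responders | Rate | Exact 95% CI |
|---|---|---|
| 18/71 (strict, assumed) | 25.4% | 15.8–37.1% |
| 20/71 (2 converters) | 28.2% | 18.1–40.1% |
| 22/71 (4 converters) | 31.0% | 20.5–43.1% |

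**3. Effect on the ROC.** Simulation of a two-sided Mann-Whitney test at 5%: 60 patients, 15 strict responders (the plan's 25% case), binormal scores with AUC 0.73. Converters are added to the responder label under two opposite assumptions about their mutational load.

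| Converters | No signal: power under the rule | Like other responders: power under the rule | Like other responders: power under a strict label |
|---|---|---|---|
| 0 | 79% | 79% | 79% |
| 2 | 72% | 83% | 75% |
| 4 | 63% | 85% | 71% |
| 6 | 57% | 87% | 65% |

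The expected AUCs follow by weighting. With no signal, the rule gives (15 × 0.73 + k × 0.5)/(15 + k) = 0.70, 0.68 and 0.66 for k = 2, 4 and 6. If converters resemble other responders, the rule leaves the AUC at 0.73. The strict label then gives [(45 − k) × 0.73 + k × 0.5]/45 = 0.72, 0.71 and 0.70, because true signal sits among the labelled non-responders.

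**4. Crossover, from the text.** Section 4.2 allows crossover after progression confirmed at least 4 weeks later with a further increase of at least 10%. Alternatively, it allows crossover when the radiologist and treating physician find unequivocal progression and the principal investigator has been consulted. Neither route describes the pseudoprogression that the rule is meant for. But the rule's operative words require only early progression, judged benefit and later confirmed conversion. They name neither the treatment under which conversion occurs nor a closing date.

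**5. PFS, from the text.** Under section 12.0, progression that is not confirmed is not an event even without the rule. Under section 14.0 the unqualified date of progression would be an event, and the rule then removes it. The two sections can give different PFS times for the same patient.

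**The case against.** The rule is pre-specified, reasoned and stated twice, beside the endpoint that it modifies. Judged benefit is a further condition on top of confirmed radiographic response, so it cannot create a response by itself. This stands: nothing is hidden, and the fault lies in the label, the undefined terms and the missing strict analysis.

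Four stronger readings are tempting, and the documents do not support them.

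- *Crossover responders will be counted as monotherapy responders.* The rationale is immune infiltration, crossover normally needs confirmed or unequivocal progression, and section 2.0 gives combination response its own numbered part. What remains is the lack of an express exclusion.
- *The rate is inflated against the external rates it will be tested against.* Section 14.0 states no null rate, historical control or test for response. Section 3.0 says only that another cohort may serve as a reference.
- *The rule weakens the ROC analysis.* That holds only if converters carry no mutational-load signal. If they resemble other responders, as the trial's hypothesis would suggest, the strict label is the one that loses power.
- *The rule lengthens PFS by erasing first progressions.* Section 12.0 already dates PFS at confirmed progression, so part of that effect comes from a separate definition.

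It is also fair that replacing the primary definition now would be a late endpoint change. The study is open label, and section 4.2 says that, as of Amendment 21, patients on active follow-up should come off study ahead of closure. That argues for showing both versions.

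**Conclusion.** The concern holds as a mismatch between label and rule. As written, the RECIST 1.1 response rate equals or exceeds the strict rate by 1.4 points per converter of 71. With 2 to 4 converters on an assumed 18/71, that is 2.8 to 5.6 points, well inside the confidence interval but a change in what the rate means. The size rests entirely on assumed counts. The ROC analysis is sensitive to the label in either direction (57% to 87% power at 6 converters under the rule), so neither label can be called the safe one. The crossover gap is an omission in the wording; the documents do not show an intention to count such responses. The PFS conflict between sections 12.0 and 14.0 is real but concerns a non-primary endpoint.

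**What to change.** 1. For the monotherapy response rate and the ROC label, count only responses reached before any crossover combination dose. Count later responses under the combination part of the objective.
2. Use the name RECIST 1.1 only for the strict best confirmed response before first RECIST 1.1 progression. Report beside it the rate that includes conversions after progression, labelled modified or immune-related, with its entry terms defined and the number of converters given.
3. Run the ROC analysis, including the Youden cut-off, under both labels.
4. Reconcile the PFS event in section 12.0 with that in section 14.0. Report PFS dated at first RECIST 1.1 progression beside the version under the rule.

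The change is to analysis wording and needs no new scans or patients. It costs one extra set of analyses and possibly a slightly lower rate under the RECIST 1.1 name. Given the late stage and open-label design, the amendment should say that both versions are reported, so that neither silently replaces the other.

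### Does a target of 10 matched biopsy pairs per tumor type, with only 10 melanoma patients enrolled, call for a change to the plan?

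*Combined protocol and SAP*

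**What the plan says.** Section 14.0 gives accrual as "A total of 81 patients will be accrued to this study (10 melanoma patient and 71 bladder" patients. After allowing for losses, including "an approximate 10% failure rate related to the biopsy, biopsy sample preparation and sequencing", it expects "approximately 60 bladder patients and approximately 8 melanoma patients with both clinical and research (genomic) data".

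The cohorts have different roles: "Only patients with bladder cancer will be evaluated for the primary and secondary objectives as described here". The next sentence adds: "Melanoma and bladder patients will be evaluated for the exploratory endpoints described in the next section". Later under the same heading, after the ROC method, it says: "This analysis of the relationship between mutation burden and response rate will be performed for each tumor type independently".

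The tissue and blood markers are introduced with this condition: "The following endpoints will be evaluated in an exploratory fashion as sample availability permits". The first of them is the paired-biopsy comparison: "We aim to collect ~ 20 matched tumor biopsies (pre-treatment/on treatment) (target 10 per tumor type), and the comparison will be primarily descriptive". The section names the Wilcoxon signed rank test as an example of the method. Endpoint 5 lets a whole-exome cut-off, if one emerges, guide a preliminary IMPACT analysis.

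Three other places matter. Section 4.1 states that the melanoma cohort is analyzed descriptively, and says the same of the ROC and Youden results by tumor type. Section 2.0 lists the paired comparison as a secondary correlative objective. Flowchart 2 in section 10.1 marks the melanoma biopsies at 2 weeks and at progression as optional.

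**The concern.** The melanoma half of the pair target equals the whole melanoma enrolment and exceeds the number expected to have usable genomic data, although the second biopsy may be refused. An equal split does not fit a 10/71 enrolment.

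Section 14.0, read alone, also seems to pull two ways. It reserves the primary and secondary objectives for bladder, then applies the mutation-burden analysis to each tumor type. It does not say whether melanoma and bladder pairs are pooled in the signed rank test, although the cohorts start on different regimens. It does not say which tumor type supplies a cut-off for IMPACT. Section 2.0 calls the paired comparison secondary while section 14.0 calls it exploratory, and that label bears on whether melanoma is included.

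At stake would be an exploratory aim that is missed, and a melanoma cut-off from about 8 patients that is read as a finding or carried into the IMPACT work.

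**Working it through.** **The plan's own figures.** Evaluable patients: 0.85 × 71 = 60.35 and 0.85 × 10 = 8.5, matching the stated 60 and 8. The bladder power statement also reproduces. With a two-sided 5% test and the Obuchowski binormal variance, power is 0.796, 0.785 and 0.789 at AUC 0.70, 0.71 and 0.73 (responders/non-responders 30/30, 20/40, 15/45). It uses bladder patients only.

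**Melanoma pairs collected.** The documents give no uptake *u*, so it is assumed, with one pair per patient and independent decisions. Expected pairs = 10*u*; chance of all ten = *u*^10.

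| Uptake | Expected pairs | Chance of 10 |
|---|---|---|
| 90% | 9 | 0.349 |
| 80% | 8 | 0.107 |
| 70% | 7 | 0.028 |
| 50% | 5 | 0.001 |

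**Melanoma pairs usable for sequencing, at full uptake.** If the 10% failure rate applies once per patient, the chance of ten is 0.90^10 = 0.349. If it applies to each of the two biopsies, it is (0.9 × 0.9)^10 = 0.81^10 = 0.122, with 8.1 pairs expected. Both readings are assumptions.

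**Bladder and overall.** Ten bladder pairs need 10/71 = 14% uptake, or 10/(71 × 0.81) = 17% allowing for failure of either biopsy. Twenty pairs overall need 20/81 = 25%. At equal uptake that gives 20 × 71/81 = 17.5 bladder and 20 × 10/81 = 2.5 melanoma pairs. The total is reachable; only the split is out of line.

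**What melanoma could show.**
- AUC, 95% half-width under no association, 1.96 × √[(n1 + n0 + 1)/(12 n1 n0)]: for 4 v 4, 1.96 × √(9/192) = 0.42; for 6 v 2, 0.49. For bladder at 20 v 40, 1.96 × √(61/9600) = 0.16.
- Maximum Youden index of 0.5 or more under no association, by exact enumeration for 8 patients: 0.400 (4 v 4), 0.232 (5 v 3), 0.464 (6 v 2). With 60 patients, by permutation, it is 0.0025 or less.
- Signed rank test, smallest two-sided p = 2/2^n: 0.0625 with 5 pairs, 0.031 with 6.

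Melanoma results can therefore only be descriptive, which is the status section 4.1 gives them.

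**Does anything depend on the target?** The power statement does not use matched pairs. No analysis is made conditional on reaching 10. No decision follows from the paired comparison. A shortfall is covered by the sample-availability condition.

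**The case for a change.** The best case for a change is that a few words would remove every ambiguity. Section 14.0 could state one overall pair aim, mostly from bladder. It could repeat that melanoma is descriptive, restrict tests and cut-offs to bladder, and name bladder as the source of any IMPACT cut-off. The Youden figures show that an 8-patient cut-off often looks useful by chance, and calling it descriptive does not prevent its reuse.

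The equal split is indeed a poor fit to the enrolment, and section 14.0 would read better with the sentence from section 4.1 repeated. The rest is weaker.

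- The need for complete uptake holds only if each patient gives one pair. Flowcharts 2 and 3 also offer optional biopsies at progression and during reinduction, and the plan does not say which may form a pair.
- The label question has an answer within section 14.0: the comparison sits under the exploratory endpoints, melanoma is admitted to those, and the target is set by tumor type.
- For the marker methods, section 14.0 refers to Appendix 3, which is listed but is not in the text available here. Pooling cannot be called unaddressed on that basis.
- The IMPACT step is conditional and preliminary. Analysts holding about 60 bladder and 8 melanoma patients can be expected to report the source of any cut-off.
- Section 4.1 expressly plans the ROC analysis for both tumor types. Dropping the melanoma AUC, cut-off and tests is a preference on which statisticians may differ, and it would remove planned descriptive output.
- Section 4.2 records that patients in active follow-up are being taken off study ahead of closure, so a revised collection target would have little practical effect.

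**Conclusion.** No change follows. The melanoma pair target is optimistic to the point of being a drafting slip: it equals the full cohort of 10 and exceeds the 8 or so expected to have usable data. At assumed uptakes of 50% to 90%, and one pair per patient, the chance of collecting all ten runs from 0.1% to 35%. But it is an approximate aim in a descriptive, hypothesis-generating comparison, and the total of about 20 needs only 25% uptake across the study.

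The status of the melanoma ROC and cut-off is settled in section 4.1 of the same document. Its absence from section 14.0 is editorial. The open points on pooling and on the source of an IMPACT cut-off are details of exploratory analyses that analysts can fill sensibly and report. The bladder response rate, the bladder AUC analysis with its power, and the safety reporting are all unaffected. This conclusion does not depend on the assumed uptake or on how the 10% failure rate is applied.

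### For IMPACT versus whole exome, correlation is the only statistic specified; no measure of high/low agreement and no way to carry an exome cutoff to IMPACT counts is given in the supplied text

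*Combined protocol and SAP*

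**What the plan says.** Secondary Correlative Objective 6 (Section 2.0) is to "Compare IMPACT assay to whole exome sequencing for the evaluation of patients according to mutation burden". Section 14.0 handles it as item 5 of the exploratory tumor and blood markers. Mutations are to be counted by each assay, and "correlation analysis between whole exome analysis and IMPACT will be assessed". The type of coefficient is not stated. The plan adds "This will be exploratory".

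The item then looks ahead to a high/low use: "If a cutoff of high versus low mutation burden is determined from earlier analyses using the whole exome", then "this will be used to guide the IMPACT preliminary analysis". Elsewhere in Section 14.0 the exome cutoff is to come from Youden's index in the ROC analysis of response.

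Two general statements cover all the exploratory markers: "Descriptive statistics and graphical measures will be employed" and "Details related to methods are described in Appendix 3". Appendix 3 is listed in Section 20.0 as laboratory procedures; its text is not among the supplied documents.

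**The concern.** The objective is about evaluating patients by mutation burden, and the plan expects a high/low cutoff to play a part. The natural question is therefore whether the two assays put the same patient in the same group. Correlation answers a different question, namely whether the two counts rise together. Both Pearson and Spearman coefficients are unchanged if every count from one assay is multiplied by a constant, so a systematic difference in calling leaves no trace.

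There is also a gap in the step from exome to IMPACT. If IMPACT covers less sequence than the exome, an exome count threshold has no direct meaning on its scale, and the supplied text gives no conversion. At stake is the reading of this objective: a high coefficient could be taken as reassurance about classification that it does not give.

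**Working it through.** **Figure to reproduce.** The plan gives no sample size, target correlation or agreement threshold for this comparison, so there is none.

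**Inputs from the documents.**
- About 60 bladder patients with clinical and genomic data (Section 14.0). This follows from 71 x 0.85 = 60.35. How many will have an IMPACT result is not stated.
- Illustrative exome cutoff of 250 mutations, about the median (Section 3.0, rationale for evaluating mutations). It comes from a retrospective ipilimumab melanoma series and is not this trial's cutoff.

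**Assumptions (not in the documents).** IMPACT is a targeted panel that sees 2-5% of exome mutations. Burden is log-normal with median 250 and log-SD 0.8-1.0. Counts are Poisson. Over-calling of 1.5- or 2-fold is hypothetical.

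**Step 1: agreement implied by a correlation when there is no bias.** For bivariate-normal log counts with correlation r, both cut at the median, agreement = 1/2 + arcsin(r)/π. Chance agreement is 0.5, so kappa = (agreement - 0.5)/0.5.
- r = 0.90: 0.5 + 1.120/3.142 = 0.856; kappa = 0.71.
- r = 0.95: 0.5 + 1.253/3.142 = 0.899; kappa = 0.80.

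**Step 2: same correlation, one assay shifted downwards (simulation).** At r = 0.90:

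| Shift (SD) | Agreement | Kappa | Sensitivity |
|---|---|---|---|
| 0 | 85.7% | 0.71 | 86% |
| 0.5 | 78.6% | 0.57 | 59% |
| 1.0 | 65.7% | 0.31 | 32% |

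The correlation is 0.90 in every row.

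**Step 3: count model, no bias, cutoff rescaled in proportion.** The rescaled cutoff is 250 x panel share: 5 mutations at 2%, 7.5 at 3%, 12.5 at 5%. With 2,000 runs of n = 60 per setting, over shares of 2-5% and log-SD 0.8-1.0, Spearman is about 0.84-0.95 and 9-17% of patients change group. Kappa is about 0.66-0.82, in line with 1 - 2 x 0.17 = 0.66 and 1 - 2 x 0.09 = 0.82. This discordance is counting noise alone.

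**Step 4: count model with over-calling** (share 3%, log-SD 0.9, cutoff 7.5):

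| Over-call | Spearman | Patients changing group | Kappa |
|---|---|---|---|
| none | 0.90 | 12% | 0.75 |
| 1.5-fold | 0.93 | 18% | 0.64 |
| 2-fold | 0.94 | 26% | 0.47 |

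Spearman improves slightly because, in this model, over-calling adds counts and so reduces relative noise. Classification worsens at the same time. If the cutoff is instead calibrated to the panel's own scale, kappa in the two biased rows is about 0.79 and 0.82.

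**Step 5: precision of an agreement analysis at n = 60.**
- Agreement, exact 95% CI: 48/60 (80%) gives 67.7-89.2%; 54/60 (90%) gives 79.5-96.2%.
- Kappa at 50% prevalence: SE = sqrt[po(1 - po)/(n x 0.25)], where po is the observed agreement. For po = 0.90, SE = sqrt(0.09/15) = 0.077, so kappa 0.80 has a CI of 0.65-0.95. For po = 0.80, SE = sqrt(0.16/15) = 0.103, so kappa 0.60 has a CI of 0.40-0.80.

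**The case against.** The strongest reply is that the plan leaves room for what is asked. It foresees an exome cutoff guiding the IMPACT work, allows descriptive and graphical methods for all these markers, and refers to Appendix 3 for detail. It calls the analysis exploratory and preliminary, sets no success criterion, and makes no treatment or eligibility decision depend on it. The cutoff may never be found. All of this lowers the importance. It does not make correlation answer a classification question: the general allowance commits to no agreement measure, whereas items 1 to 3 of the same list name specific tests. Appendix 3 could hold a conversion or concordance method, so the gap can be asserted only for the supplied text.

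The numbers are also open to challenge, and part of that challenge stands. Without bias, high correlation goes with reasonable agreement. The low kappas need both an assumed over-call and a cutoff not calibrated to the panel, and nothing in the documents suggests that IMPACT over-calls. Per-megabase scaling alone would expose such a bias, not remove it.

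A reader might infer that the exome count will be applied unscaled to IMPACT counts. In the model that gives about 50% agreement and kappa near zero, since at a 3% share a panel count of 250 needs 250/0.03 = about 8,300 exome mutations. But the plan says guide, not apply.

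**Conclusion.** The point holds, at low importance. In the supplied text, correlation is the only statistic specified for this comparison, and neither an agreement measure nor a way to carry the exome cutoff across is given. That correlation cannot reveal a constant scale difference is a mathematical fact and needs no assumption. The size does rest on assumptions: 9-17% of patients changing group under counting noise alone, and more only under hypothetical bias. The cutoff of 250 is illustrative; this trial's cutoff would be estimated by Youden's index, mainly in bladder cancer.

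Two stronger readings are not supported. A reader might infer that the plan ignores classification altogether; the sentence on the cutoff shows otherwise. A reader might also infer that IMPACT is meant to replace exome sequencing on the strength of a high correlation; no section says so.

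**What to change.** In Section 14.0, item 5:
- Express both assays as mutations per megabase covered, or state how the cutoff will be calibrated to the panel scale. A cutoff calibrated and assessed in the same patients will look optimistic and should be labelled so.
- If an exome cutoff is found, report a 2x2 high/low table with exome as reference, giving positive and negative percent agreement and kappa with 95% CIs.
- Add a log-scale Bland-Altman plot, which shows systematic bias whether or not a cutoff is found.
- Keep correlation as a descriptive measure and name the coefficient.
- If Appendix 3 already covers this, a cross-reference is enough.

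The cost is a few extra lines of analysis on data already planned, with no new patients or samples. The downside is wide intervals at about 60 patients, as shown in the working, so the results should be reported as estimates and not as a pass or fail.
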